In the ROM+DEX arm, starting romiplostim dose will be 3 mcg/kg, adjusting the following weekly doses according to platelet counts following actual label indications (see section Dosage an administration, for more detailed information). Patients will weekly receive dose increases of romiplostim in increments of 1 mcg/kg up to a maximum dose of 10mcg/kg aiming for a platelet count higher than 50 x10⁹/L. If romiplostim dose is stable for 4 weeks and platelets are higher than 50x10⁹/L, romiplostim will be tapered in 1 mcg/kg per week to a dose of 1 mcg/kg per week. If after 4 additional weeks, platelets remain greater than 50, the Interval between 1mcg/kg romiplostim injections will increase to 14 days. If after another 4 doses, platelets remain >50x10⁹/L, romiplostim should be discontinued. If after 4 doses of romiplostim 1 mcg/kg/14 days, platelets remain still higher than 50x10⁹/L treatment with romiplostim should be ended.

Otherwise, if platelets are lower than 50x10⁹/L, treatment with romiplostim will continue until 365 days after randomisation.

If platelets are between 50-100x10⁹/L, investigator will take the decision to stop or not romiplostim according to patient's risk of bleeding. This decision will be always taken after discussion with the study coordinator.

If patient needs treatment again it will be prescribed according to routine clinical practice. In romiplostim is used, it will not be supplied by the sponsor.

In the ROM+DEX arm, dexamethasone will be administered 40 mg daily x 4 days only in the first cycle. Gastric protection alongside dexamethasone is

recommended. Romiplostim first dose could be administrated day 1, 2, 3 or 4 of first cycle of dexamethasone.

In the DEX arm, dexamethasone will be administered 40 mg daily x 4 days for up to 3 cycles every 14 to 28 days. No dose adjustment for dexamethasone is permitted. Gastric protection alongside dexamethasone is recommended.

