The risks are those inherent in the usual treatment of ITP, the benefit is the earlier access to the use of thrombopoietin analogues, reducing the long-term side effects of steroids, which have been shown to be greater than those of steroids. In addition, the potential benefit is that the early combination of two types of ITP treatment that act via different pathways may improve ITP treatment outcomes by reducing the rate of chronicity, which with steroid monotherapy is 60% at 6 months post-treatment cessation

iv. Romiplostim

The indications for romiplostim have recently been updated. Romiplostim is indicated for the treatment of primary immune thrombocytopenia (ITP) in adult patients who are refractory to other treatments (e.g., corticosteroids, immunoglobulins).

Romiplostim is a peptibody that includes a carrier domain (IgG1 Fc portion) and a peptide-containing domain (four peptides, each comprising 14 amino acids, designed to activate the TPO receptor [c-mpl; TPO-R] but avoid production of antibodies that can bind to endogenous TPO) [21–23] due to romiplostim has no amino acid sequence homology to endogenous TPO (eTPO). The peptides bind to the extracytoplasmic domain of the TPO-R and activate the receptor similarly to that of endogenous TPO, meaning that romiplostim and endogenous TPO compete for receptor binding [22,23].

For a complete summary of safety and efficacy data collected for the romiplostim clinical development program, please refer to the most recent version of the Investigator's Brochure.

Clinical efficacy and safety

In clinical trials, treatment with romiplostim resulted in dose-dependent increases in platelet count. Time to reach the maximum effect on platelet count is approximately 10-14 days, and is independent of the dose. After a single subcutaneous dose of 1 to 10 mcg/kg romiplostim in ITP patients, the peak platelet count was 1.3 to 14.9 times greater than the baseline platelet count over a 2 to 3 weeks period and the response was variable among patients. The platelet counts of ITP patients who received6 weekly doses of 1 or 3 mcg/kg of romiplostim were within the range of 50 to 450x10⁹/L for most patients.

Results from pivotal placebo-controlled studies

The safety and efficacy of romiplostim was evaluated in two placebo-controlled, double-blind studies in adults with ITP who had completed at least one treatment

prior to study entry and are representative of the entire spectrum of such ITP patients.

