hours in a refrigerator ($2^{\circ}C - 8^{\circ}C$) when the diluted product was held in the original vial.

From a microbiological point of view, the diluted romiplostim should be used immediately. If not used immediately, in-use storage times and conditions prior to use are the responsibility of the user and would normally not be longer than 4 hours at 25° C in disposable syringes, or 4 hours in a refrigerator (2° C – 8° C) in the original vials, protected from light.

Dexamethasone

Dexamethasone does not require special storage conditions in terms of temperature. Store in the original pack to protect from light and moisture.

Any unused medicine or waste material should be disposed of in accordance with local requirements.

b. Dosage and administration

Romiplostim

Romiplostim will be administered in the clinic by a qualified healthcare provider as a subcutaneous (SC) injection until the patient is ready to self-administer, according to medical criterion. Self-administration will be registered in medical records. In the ROM+DEX arm, starting romiplostim dose will be 3 mcg/kg, adjusting the following weekly doses according to platelet counts following actual label indications.

Dosage calculation

The starting dose of romiplostim is 3mcg/kg which is calculated based on current body weight (Table 1).

Table 1. Romiplostim dose calculation

Initial or subsequent doses once a a week	Weight* (kg) x dose (mcg/kg) = individual patient dose (mcg)
Volume of administration:	Doses (mcg) x $\frac{1 ml}{500 mcg}$ = quantity to be injected (ml)
Example:	 The starting dose for a 75 kg patient is 3mcg/kg romiplostim. Individual patient dose= 75 kg x 3mcg/kg = 225 mcg Corresponding amount of romiplostim solution to be injected: 225 mcg x 1ml/500 mcg = 0,45 ml to be injected

*The current body weight of the patient at the time of initiation of treatment should always be used when calculating the dose of romiplostim. Future dose adjustments should be based solely on changes in platelet counts and should be made in 1 mcg/kg increments.

Dosage adjustment

Table 2 Dose adjustments and tapering

platelet counts	Romiplostim dosage adjustment					
Platelets <50x10 ⁹ /L	Increase 1mcg/kg/week to a maximum of 10mcg/kg/week					
Platelets 50-	No change in dose.					
250x10 ⁹ /L	Drug tapering:					
	 If 4 consecutive weeks with stable dose, reduce romiplostim in 1mcg/kg/week. 					
	 If stable dose during 4 weeks is 1mcg/kg/week, reduce romiplostim to 1mcg/kg/14 days. 					

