	 If stable dose is 1mcg/kg/14 days after 4 doses stop romiplostim 					
Platelets >250x10 ⁹ /L	Stop romiplostim and platelet control weekly.					
	 Restart romiplostim when platelets < 150x10⁹/L 					
	 Restart romiplostim at 1mcg/kg/weekly less than previous 					

- 1. The starting dose should be 3 mcg/kg/week*. It could be start during de 4 days of dexamethasone. This dosage is due to:
 - The patient profile, on whom it is urgent to achieve an effective treatment as soon as possible.
 - Current clinical practice. PTI Spanish clinical guideline [43] recommends starting with a dose of 5-10 mcg/kg in urgent cases. In the Spanish PTI guideline also it is stated that "although Romiplostim is initiated according to prescribing information at a dose of 1 μg/kg/week subcutaneously, most patients require doses of 3 μg/kg/week to respond, so in clinical practice it is usually initiated at 3 μg/kg/week, reaching a maximum dose of 10 μg/kg/week."
 - Other clinical study [44] with similar patient profiles the median dose (Q1-Q3) of romiplostim was 2,6(1,6-3,9)mcg/kg.

*Since the starting dose of romiplostim will be 3 mcg/kg instead of 1 mcg/kg as indicated in the label, close monitoring of potential safety concerns will be conducted.

- 2. Patients will weekly receive dose increases of romiplostim in increments of 1 mcg/kg up to a maximum dose of 10 mcg/kg in an attempt to reach a target platelet count higher than 50x10⁹/L.
 - If romiplostim dose is stable for 4 weeks and platelets are higher than 50x10⁹/L, romiplostim will be tapered in 1 mcg/kg per week up to a dose of 1 mcg/kg per week.
 - If after 4 additional weeks patients still present platelet counts higher than 50x10⁹/L with romiplostim 1 mcg/kg, romiplostim will be indicated as 1 mcg/kg/14 days.
 - If after 4 doses of romiplostim 1 mcg/kg/14 days, platelets remain still higher than 50x10⁹/L treatment with romiplostim should be ended.
- 3. Otherwise, if platelets are lower than 50x10⁹/L treatment with romiplostim will go on until Day 365 since randomization.

If platelets are between 50-100x10⁹/L, investigator will take the decision to stop or not romiplostim according to patient's risk of bleeding. This decision will be always taken after discussion with the study coordinator.

Dexamethasone

Dexamethasone will be given to the patient for oral administration at home.

In the ROM + DEX arm, dexamethasone will be administered 40 mg daily x 4 days only in the first cycle

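### After 4 stable weeks with a count above 250x10⁹/L, the taper text in 9.b orders a further romiplostim dose while Table 2 orders a stop, and Table 2's restart line has no lowest dose

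*Protocol*

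**What the plan says.** Table 2 in 9.b sorts patients by platelet count. In the 50-250x10⁹/L row the dose is held, and after 4 weeks at a stable dose it is tapered by 1 mcg/kg/week. From a stable 1 mcg/kg/week the instruction is "reduce romiplostim to 1mcg/kg/14 days", and after four such doses romiplostim stops. These steps appear only in that row. Above 250x10⁹/L the instruction is "Stop romiplostim and platelet control weekly", with a restart once the count is below 150x10⁹/L, as follows: "Restart romiplostim at 1mcg/kg/weekly less than previous".

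Item 2, beneath the table, describes the same taper with a lower limit only. The first step applies after 4 stable weeks with a count over 50x10⁹/L. The second reads "If after 4 additional weeks patients still present platelet counts higher than" 50x10⁹/L on 1 mcg/kg, "romiplostim will be indicated as 1 mcg/kg/14 days". Sections 1.h and 6.a repeat both steps, again without a ceiling; each says that "the Interval between 1mcg/kg romiplostim injections will increase to 14 days". Neither mentions the stop above 250x10⁹/L, and both send the reader to the dosage section for detail.

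The footnote to Table 1 says that later dose changes "should be made in 1 mcg/kg increments". Section 9.d refers back to 9.b as a whole and gives no order of precedence.

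**The concern.** At one and the same visit, the text and the table can give opposite orders. A patient who has had 4 weeks on 1 mcg/kg/week and presents at 300x10⁹/L gets another injection under item 2 and none under Table 2. A site that follows Table 2 then meets a second gap. When the count falls below 150x10⁹/L it is told to restart, but the restart dose computes to zero.

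The stake is patient safety and uniform dosing. Thrombotic and thromboembolic events are listed in 10.c.vii as adverse events of special interest for romiplostim. Section 9.b also promises close safety monitoring because treatment starts at 3 mcg/kg, against 1 mcg/kg in the label. Whether a held patient is restarted also determines when treatment has ceased, and the primary endpoint is counted from that date. Two sites could therefore date cessation differently for the same counts.

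**Working it through.** No stated figure is being reproduced here. The check applies both rules to the same patient states and compares the orders.

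**Inputs, all from 9.b**
- Table 2: taper only at 50-250x10⁹/L after 4 stable weeks; stop above 250x10⁹/L; restart below 150x10⁹/L at the previous weekly dose minus 1 mcg/kg.
- Item 2: taper after 4 stable weeks if the count is above 50x10⁹/L; floor of the taper 1 mcg/kg/week, then 1 mcg/kg/14 days; end after four 14-day doses.

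**Step 1. Orders after 4 weeks at a stable dose**

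| Count (x10⁹/L) | Current dose (mcg/kg/week) | Table 2 | Item 2 |
|---|---|---|---|
| 100 or 250 | 5, 3, 2 | 4, 2, 1 | 4, 2, 1 |
| 100 or 250 | 1 | 1 mcg/kg/14 days | 1 mcg/kg/14 days |
| 251 or 300 | 5, 3, 2 | stop | 4, 2, 1 |
| 251 or 300 | 1 | stop | 1 mcg/kg/14 days |

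The rules agree at every dose up to 250x10⁹/L and disagree at every dose above it.

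**Step 2. When the conflict arises.** With fewer than 4 stable weeks, item 2 gives no order above 250x10⁹/L, so only Table 2 speaks. For a site that applies Table 2 throughout, an earlier count above 250x10⁹/L would already have stopped the drug. For that site the overlap is therefore a first crossing of 250x10⁹/L at or after the 4-week mark.

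**Step 3. Restart dose under Table 2** (previous weekly dose minus 1)
- 5 − 1 = 4; 3 − 1 = 2; 2 − 1 = 1; 1 − 1 = 0 mcg/kg/week.
- From the 3 mcg/kg starting dose, successive holds without re-escalation give restarts at 2, 1 and 0, so the third hold reaches zero.
- From 1 mcg/kg/14 days, the weekly average is 1/2 = 0.5 and 0.5 − 1 = −0.5, which is not a dose.

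With changes made in steps of 1 mcg/kg, nothing lies between 1 and 0. The move to a 14-day interval is offered only in the 50-250 row. The only stated floor, 1 mcg/kg/week, belongs to item 2's taper and not to the restart.

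**Step 4. The ending step.** After the fourth 14-day dose with a count above 250x10⁹/L, both rules withhold the drug at that visit. Item 2 ends treatment, whereas the >250 row read alone is a hold with a possible restart. Item 2 is the natural rule to govern here, but the row does not say so.

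**Step 5. After a correction.** If the two item 2 steps are limited to 50-250x10⁹/L, the disagreement in the last two table rows disappears. With a floor of 1 mcg/kg/week, taken as an example, the restart from 1 becomes max(1, 1 − 1) = 1. A restart from 1 mcg/kg/14 days still needs its own rule.

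**The case against.** The strongest reply is that the documents should be read together. Item 2 gives the same three steps in the same order as Table 2's 50-250 row, so it can be taken as a narrative of that row, with the >250 row as the exception. Sections 1.h and 6.a are summaries that defer to 9.b, so they are not two further independent contradictions. Much of this stands: many sites would probably follow the table. But precedence has to be inferred, and the reply does nothing for the restart line, which fails for a site that follows Table 2 exactly.

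A second reply is that 1.h, 6.a and 9.b say weekly doses are adjusted in line with the label, which might supply a minimum dose. The label is not at hand, so this cannot be checked. The absence of a floor is established for the protocol text only.

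A third is that sites are not left alone, since the protocol names a medical monitor and requires discussion with the study coordinator for stopping decisions at 50-100x10⁹/L. That shows a channel exists, but the rule does not extend to counts above 250x10⁹/L.

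Two stronger readings are tempting and are not supported. A reader might infer that a later last dose uses up part of the 180-day primary window. It does not: the window starts at each patient's own cessation, so it moves and is not shortened. A reader might also infer a long run of injections above the threshold by following item 2 through the whole taper. That would need a count above 250x10⁹/L and a site ignoring the >250 row at every visit, and nothing in the protocol makes that likely.

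**Conclusion.** The point holds in two limited parts. First, after 4 weeks at a stable dose with a count above 250x10⁹/L, item 2 of 9.b and its summaries order a further dose where Table 2 orders a stop. No precedence is stated, although Table 2 is the more specific rule. Second, Table 2's restart line gives 0 from 1 mcg/kg/week and nothing defined from 1 mcg/kg/14 days.

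The size is minor and the frequency unknown. The protocol gives no share of patients above 250x10⁹/L at these doses. Section 5.a.iv reports that counts on 6 weekly doses of 1 or 3 mcg/kg "were within the range of 50 to 450x10⁹/L for most patients". That makes the situation foreseeable but does not quantify it. The low doses concerned are ordinary ones, since every patient who completes the taper passes through 1 mcg/kg/week and the 14-day doses. No effect on the 6mSROT-50 rate is claimed. The conclusion rests on the protocol text alone and assumes that the label reference does not silently supply a floor.

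**What to change.** 1. In item 2 of 9.b, and in the matching sentences of 1.h and 6.a, write the two dosing steps for counts of 50-250x10⁹/L, as Table 2 does, and add: *Above 250, follow the >250 row of Table 2.*
2. In the >250 row, state a lowest restart dose. For patients held at 1 mcg/kg/week the sponsor should choose either 1 mcg/kg/week or 1 mcg/kg/14 days; the protocol does not settle which. State also what applies to patients held at 1 mcg/kg/14 days.
3. If a sentence is added that treatment has ended after the fourth 14-day dose, limit it to counts above 100x10⁹/L, including those above 250x10⁹/L. A wider sentence would collide with the investigator's decision at 50-100x10⁹/L, which should stay as it is.

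The cost is a few lines of text in three sections and one dosing choice by the sponsor. Section 13.d requires an amendment for any change to the protocol, so this is best bundled with the next one. Arms, visits, endpoints and sample size are unchanged.

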- To evaluate the difference between study arms in the proportion of patients achieving 12mSROT-30 at 12 months (365 days) from treatment cessation.
 - Definition of 12mSROT-30: platelets higher or equal than 30x10⁹/L in the absence of any ITP treatment including any rescue treatment for at least 12 consecutive months (≥365 days) from treatment cessation and without WHO grade 2 or more bleeding.
- To evaluate the difference between study arms in the proportion of patients with complete response (CR) at 6 months (Day 180), at 12 months (Day 365) from randomisation and at End of study Visit (visit 12 months after the last dose of study treatment). We will evaluate this in the total sample and in the absence of any rescue treatment
 - Definition of CR: platelet count ≥100x10⁹/L and absence of bleeding symptoms.
- To evaluate the difference between study arms in the proportion of patients with response (R) at 6 months (Day 180), at 12 months (Day 365) from randomisation and at End of study Visit (visit 12 months after the last dose of study treatment). We will evaluate this in the total sample and in the absence of any rescue treatment
 - Definition of R: platelet count between 100x10⁹/L and 30x10⁹/L and at least doubled from baseline and absence of bleeding symptoms.
- To evaluate the difference between study arms in the proportion of patients with global response (GR) at 6 months (Day 180), at 12 months (Day 365) from randomisation and End of study Visit (visit 12 months after the last dose of study treatment). We will evaluate this in the total sample and in the absence of any rescue treatment
 - Definition of GR: CR or R.
- To evaluate the difference between study arms in the proportion of patients with response within the target range (TR) at 6 months (Day 180), at 12 months (Day 365) from randomisation and End of study Visit (visit 12 months after the last dose of study treatment). We will evaluate this in the total sample and in the absence of any rescue treatment
 - o Definition of TR: platelet count between ≥30x10⁹/L and ≤400x10⁹/L.

- To evaluate the difference between study arms in the median time to first response defined as the time from randomization to first response (R) in the absence of any rescue treatment. We will evaluate this in the total sample and in the absence of any rescue treatment.
- To evaluate the difference between study arms in the proportion of patients with early response (ER) and initial response (IR).

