In the DEX arm, dexamethasone will be administered 40 mg daily x 4 days for up to 3 cycles every 14 to 28 days.

The use of commercial dexamethasone will be authorized up to 3 days, in case the patient is attended in emergency care while the criteria for the study are being checked and labeled study medication is assigned.

c. Treatment duration and monitoring

The monitoring will be the same in both arms with slight differences to allow for dose adjustments of romiplostim:

In the ROM + DEX arm patients will be reviewed weekly for 8 weeks (56 days). After Week 8, patients will be reviewed every 2 weeks (14 days) for 8 additional weeks and then monthly until Week 52 (Month 12) from randomization.

- o If romiplostim dose should be modified, patients will be reviewed weekly until a stable dose of romiplostim is reached for at least 4 weeks (28 days). After that, patients will go on with visits every 2 weeks (14 days) for 8 weeks and then monthly until Week 52(Month 12) from randomization.
- In the DEX arm, patients will be reviewed weekly until the completion of dexamethasone cycles and for a minimum of 8 weeks (56 days). After that, every 2 weeks (14 days) for 8 additional weeks and then monthly until Week 52 (Month 12) from randomization.

Once romiplostim or dexamethasone is stopped or after 365 days since randomization, patients should be clinically evaluated minimum every 4+/- 1 week for 12 months and continuation of treatment should be decided on an individual basis by the treating physician.

If patient needs treatment again it will be prescribed according to routine clinical practice. In case romiplostim is used, it will not be supported by the sponsor.

d. Criteria for dose adjustments

Dose adjustments for romiplostim will be based on platelet count as described in previous Dosage and administration section.

No dose adjustment for dexamethasone is permitted.

e. Rescue medication

We will consider rescue medication IVIg, platelet transfusion or prednisone. Tranexamic acid will be not considered rescue medication. Rescue medication will be used as follow:

- In the ROM + DEX arm, if platelets counts are lower than 20x10⁹/L or bleeding symptoms related to thrombocytopenia are present between romiplostim doses, rescue therapy with IVIg(maximum dose 2 gr/kg in total during 1 to 5 days) can be used. Prednisolone is not allowed in this arm.

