- In the DEX arm, if platelet counts are lower than 20x10⁹/L or bleeding symptoms related to thrombocytopenia are present between cycles, rescue therapy with IVIg (maximum dose 2 gr/kg in total during 1 to 5 days) or low doses of prednisone (0,5 mg/kg/d) can be used. If patients use rescue treatment with prednisone, they should be decreased as soon as possible and stopped within 8 weeks.

f. Treatment failure

In the ROM + DEX arm, it would be considered treatment failure if platelets are lower than 30x10⁹/L after 4 weeks with romiplostim at 10 mcg/kg/week or rescue

medication is needed to get this level of platelets despite this dose of 10mcg/kg/week for 4 weeks.

In DEX arm, it would be considered treatment failure if platelets are lower than 30x10⁹/L after 3 cycles of dexamethasone or if rescue medication is needed to get this level of platelets despite the 3 cycles of dexamethasone.

In both arms, treatment failure will be considered to in those patients bleeding who are refractory to therapy in whom it is considered clinically in their best interests to escalate or switch treatment in a way that does not align with the protocol treatment schedules. Patients will be discussed with Steering Committee before to be considered treatment failure.

If patients lose response on the DEX arm, they can be switched from one arm to the other (to TPO-RA), but outside the trial. The treatment will be provided by their centre and this information will be collected up in the CRF. The patients will be considered a treatment failure.

g. Accountability

The study medication (i.e., romiplostim, dexamethasone) will be sent directly from the sponsor to the investigator's site pharmacy preceded by the Regulatory Green Light. The medication is to be used exclusively in the clinical trial according to the instructions of this study protocol.

When a drug shipment is received, the Investigator or designee will check the amount and condition of the delivery, drug expiration date, and sign the Receipt of Shipment Form provided. The Receipt of Shipment Form should be faxed or sent by e-mail to the CRO. The original form will preliminarily be retained at the site and will be collected at the next monitoring visit by the monitor and stored in the TMF at CRO. A copy will remain in the Investigator File at the site. In case of shipment problems, the Investigator or designee shall contact the CRA as soon as possible.

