An Investigational Product Accountability Log will be provided for the trial medication. The record must be continuously updated and contain the dates, quantities and compounds of drugs received, medication identification number(s), the patient identification number to whom the trial medication was dispensed, date and quantity of medication dispense and the initials of the dispenser.

h. Concomitant medication

Throughout the study, investigators may prescribe any concomitant medications or treatments deemed necessary to provide adequate supportive care, except for those listed in section *Prohibited drugs*.

For concomitant therapies therapy name, indication, dose, unit, frequency, route, start date and stop date will be recorded.

Reduction or discontinuation of permitted concurrent ITP therapies may begin once a subject's platelet count has increased to ≥50x10⁹/L.

Rescue medication will also be collected.

Concomitant therapies are to be collected from screening through the EOS visit, as applicable.

i. Prohibited drugs

The following medications are not permitted during this study. After treatment failure, they will be allowed:

- Other thrombopoietic receptor agonists
- Any cytotoxic agents, alkylating agents
- Rituximab
- rHuTPO
- Interferon
- Herbal supplements that are associated with bleeding side effects including, but not limited to, gingko biloba, garlic, ginseng, fish oil, dong quai, feverfew. Garlic and ginseng taken through a normal diet are not excluded.
- Aspirin at doses higher than 100mg or anticoagulant drugs.
- Treatments for ITP other than allowed rescue medications (includings plenectomy).
- Any other investigational agents that are not approved

Should a subject require administration of any of the medications listed above, sponsor should be consulted before the medication is administered, when possible. In all cases, sponsor must be informed within 24 hours. Sponsor may decide that the subjects will be ineligible to receive additional administrations of study medication.

STUDY SCHEDULE AND STUDY FLOW-CHART

Study flow-chart

[figure not shown]

Table 3. Schedule of study assessments.

DEX arm

Visit number	Visit 0 Screening	Visit 1 Baseline	Visit 2- 8	Visit 9	Visit 10, 11, 12, 13 and 15	Visit 17-18	Visit 19	Visit 20-24	Visit 25	Visit 26-36 (Periodical clinical evaluation after the end of study medication ¹¹)	Visit 37 (End of study Visit) ¹²	

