All patients who are randomized will be included in the ITT Population. The ITT Population will be used to summarize subject disposition and baseline characteristics. Patients will be analysed according to the treatment they were allocated to at randomization; not necessarily the treatment they actually received. Results will be presented "as randomized."

mITT Population

All patients who are randomized and received at least one dose of study medication will be included in the mITT Population. The mITT Population is the primary analysis population for efficacy. Patients will be analysed according to the treatment they were allocated to at randomization; not necessarily the treatment they actually received. Results will be presented "as randomized."

rITT Population

All patients who are randomized and received at least one dose of study medication and achieved response (R) at any time during the study will be included in the rITT Population. The rITT Population will be used for the analysis of time to loss of response. Patients will be analysed according to the treatment they were allocated to at randomization; not necessarily the treatment they actually received. Results will be presented "as randomized."

d. Analysis of Primary Objective

The primary endpoint is 6mSROT-50 rate at 6 months (180 days) from treatment cessation.

The proportion of patients with 6mSROT-50 and corresponding 95% CIs for each study arm will be provided. A Chi-square test or Fisher test if applicable, will be used to compare the proportion of 6mSROT-50 between treatment arms.

e. Analysis of Secondary Objectives

i. Secondary Efficacy evaluations

For the analysis of the secondary endpoints, following analyses will be conducted:

- The proportion of patients with 6mSROT-30, 12mSROT-30 and 12mSROT-50 and corresponding 95% CIs for each study arm will be provided. A Chi-square test or Fisher test if applicable will be used to compare the proportion of each endpoint between treatment arms.
- The proportion of patients with CR, R, GR or TR at 6 and 12 and End of study Visit (visit 12 months after the last dose of study treatment) will be calculated and corresponding 95% CIs for each study arm will be provided. A Chi-square test or Fisher test if applicable will be used to compare the proportion of each endpoint between treatment arms.

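### DEX failures moved to a TPO-RA can count as responders for CR, R, GR and TR even in the rescue-free analysis, because a TPO-RA is not on the rescue list

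*Protocol*

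**What the plan says.** **Response endpoints.** Sections 1.j and 6.c define CR and R by platelet count (with doubling from baseline for R) and absence of bleeding. GR is either of these, and TR is a count from 30 to 400 x10⁹/L. Section 11.e.i lists the analysis: "The proportion of patients with CR, R, GR or TR at 6 and 12 and End of study Visit". Section 1.j gives two versions: "We will evaluate this in the total sample and in the absence of any rescue treatment". Maximum consecutive days and total days in response get the same two versions. Section 11.c makes mITT, analysed as randomised, the efficacy population.

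**Rescue.** Section 9.e: "We will consider rescue medication IVIg, platelet transfusion or prednisone". A TPO-RA, rituximab and splenectomy are not listed.

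**Switching.** Section 9.f: "If patients lose response on the DEX arm, they can be switched from one arm to the other (to TPO-RA), but outside the trial". It continues: "The treatment will be provided by their centre and this information will be collected up in the CRF". And then: "The patients will be considered a treatment failure". Section 9.i, on TPO-RAs other than study drug, rituximab and further ITP treatments, says: "The following medications are not permitted during this study. After treatment failure, they will be allowed". Section 9.c leaves treatment after the end of study medication to routine practice, including romiplostim not provided by the sponsor.

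**SROT.** The primary endpoint and the other SROT endpoints require that the patient be free of every ITP treatment, rescue included.

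**Follow-up.** Section 8.b lists treatment failure as a reason for removal from the study. Section 8.c says all subjects are followed for 12 months from randomisation and for at least 6 months after stopping treatment.

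**The concern.** The rescue-free analysis is the only one offered for CR, R, GR and TR that removes the effect of added therapy. As worded, it removes patients given IVIg, platelets or prednisone but leaves in those given a TPO-RA, rituximab or another second-line treatment. A DEX patient can then be a treatment failure under 9.f and a complete responder at Day 365, in the total sample and in the rescue-free analysis alike.

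The objective in Sections 1.g and 5.c is superiority over dexamethasone alone on these endpoints. If switched patients count as responders, the DEX result describes dexamethasone followed by a TPO-RA where needed. In ROM+DEX the same gap lets a patient who restarts commercial romiplostim after study treatment count as a responder at the End of study Visit.

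**Working it through.** **The plan's own figure.** The only sample size stated is for the primary endpoint: 30% versus 56.6%, two-sided 5%, 80% power, 15% dropout, 63 per arm (Section 11.b). With the pooled-variance formula, no continuity correction and mean rate 0.433:

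n = [1.96 × √(2 × 0.433 × 0.567) + 0.8416 × √(0.30 × 0.70 + 0.566 × 0.434)]² / 0.266² = 53.3, so 54 per arm.

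Adding 15% gives 54 × 1.15 = 62.1, so 63; dividing by 0.85 gives 63.5, so 64. The stated 63 reproduces. This point does not touch it, because the primary endpoint already rules out any ITP treatment.

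**Tracing one patient through the text.** Take a DEX patient who loses response, starts a TPO-RA without IVIg, transfusion or prednisone, and at Day 365 has a count of 150 x10⁹/L and no bleeding.

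| Rule | Result |
|---|---|
| CR definition (1.j, 6.c) | met |
| Total sample, as randomised | DEX responder |
| Rescue-free analysis, using the 9.e list | no rescue given, so still a DEX responder |
| Days in response | accrue while on the TPO-RA |
| Treatment failure (9.f) | failure |
| SROT endpoints | not met while on any ITP treatment |
| Removal (8.b) versus follow-up (8.c) | the Day 365 count may be missing or present |

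The first four rows conflict with the fifth. The last row means that the text does not settle whether the count exists.

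**Possible size.** The protocol gives no rates for CR, R, GR or TR and no switch rate, so this only illustrates the mechanism. Let p be the DEX response rate without switching, s the share of DEX non-responders on a TPO-RA at the visit, and r their response on it. Then:

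observed DEX rate = p + (1 − p) × s × r

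The range r = 0.79 to 0.95 is the romiplostim figure in Section 5.a.iv. It refers to a count above 50 x10⁹/L at any visit, so it is generous for one fixed date. Values of s are assumed. ROM+DEX is held fixed. Power is for 63 per arm.

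| Assumed DEX / ROM+DEX | s | Observed DEX | Difference (points) | Power |
|---|---|---|---|---|
| 30% / 56.6% | 0 | 30% | 26.6 | 86% |
| | 10% | 35.5–36.6% | 21.1–19.9 | 66–61% |
| | 25% | 43.8–46.6% | 12.8–10.0 | 30–20% |
| 50% / 80% | 0 | 50% | 30 | 95% |
| | 10% | 53.9–54.7% | 26.1–25.3 | 88–87% |
| | 25% | 59.9–61.9% | 20.1–18.1 | 70–61% |
| | 50% | 69.8–73.8% | about 10 to 6 | 26–13% |

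Example: 0.30 + 0.70 × 0.25 × 0.79 = 0.438, and 0.566 − 0.438 = 0.128.

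The first pair of rates is borrowed from 6mSROT-50 and the second is simply assumed. At s = 50% the first pair gives −1 to −7 points. That is an artefact of crediting switched DEX patients with 79–95% while holding ROM+DEX at an off-treatment rate, so it should not be used.

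**The case against.** **The protocol never says that switched patients are responders.** A reader might infer that it does. It calls them treatment failures, does not link that status to CR, R, GR or TR, and lists failure as a reason for removal, so their later counts may be missing. This stands: the supportable claim is that they can be counted under the written definitions.

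**The rescue list is not the cause in the total sample.** Switched patients would be included there whatever 9.e listed, and an as-randomised comparison regardless of later therapy is a recognised treatment-policy approach. This also stands. The list explains only why the second analysis fails to remove added therapy.

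**The rule could be left to the analysis plan,** which Section 11.a says will be finalised before database lock. This holds only in part. The protocol requires freedom from all ITP treatment for SROT but only freedom from rescue here, so an analysis plan that follows it literally inherits the gap.

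**The treatment difference is not hidden.** A reader might infer that it is hidden or even reversed. The documents do not support that: SROT is protected, treatment failure and time to failure are separate endpoints, and Section 11.e.i declares secondary results exploratory. ROM+DEX patients may be on study romiplostim up to Day 365, and those who fail may also receive the otherwise prohibited drugs. The illustration models neither.

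**Conclusion.** The point holds as a gap in the response definitions and the rescue-free condition. Read literally, DEX patients who fail and move to a TPO-RA, and patients in either arm who start other non-protocol ITP therapy after failure or after study treatment ends, can count as responders for CR, R, GR and TR and accrue days in response in both analyses. For switched DEX patients this conflicts with 9.f.

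The gap can attenuate the comparison with dexamethasone alone, but by an unknown amount. Under the assumptions shown, switching 10% of DEX non-responders costs about 4 to 7 points, and larger shares cost more; none of these is an estimate. The primary and other SROT endpoints and the sample size are unaffected, and the endpoints concerned are exploratory. The change is worth making because it is cheap and the second analysis otherwise does not do what it is meant to do.

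**What to change.** 1. Keep the total-sample, as-randomised result for CR, R, GR, TR and days in response, labelled as a treatment-policy analysis.
2. In the second analysis, replace the rescue-free condition with freedom from rescue and from any ITP treatment outside the randomised regimen. Count as a non-responder any patient who started such outside treatment, or was declared a treatment failure, before the visit. For days in response, stop counting at that date. Non-response is preferable to exclusion, which Sections 1.g and 5.c describe for rescued patients, because exclusion would drop failures from the denominator. Handling of patients given only listed rescue is a separate matter.
3. Reconcile Section 8.b (removal for treatment failure) with Section 8.c (12-month follow-up of all subjects), so that it is clear whether counts after failure are collected.
4. Confirm that ITP therapy after Month 12 is captured. The ITP medication row in both parts of Table 3 stops there, and after Month 12 rescue medication is marked only at unscheduled visits. Section 9.h collects concomitant therapies through the end-of-study visit.

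The cost is mainly endpoint wording, with no change to sample size or treatment; 9.f already says the switch is recorded. The downside should be stated: response rates fall, mainly in DEX, since ROM+DEX patients on study romiplostim remain eligible as responders. In an open-label trial the clinician's decision to switch then determines non-response, which is why the treatment-policy result is kept alongside.
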